2. The following Erchonia-sponsored clinical study outcome supported the 510(k) clearance for application of the simultaneous *combined Erchonia red and violet laser light therapy* to the *adjunctive temporary relief of minor chronic neck and shoulder pain of musculoskeletal origin*.

The study was a single (active treatment only) group non-inferiority design to evaluate equivalency or superiority of the Erchonia® EVRL in red/violet diode combination application with red diode only application in the temporary reduction of neck and shoulder pain of musculoskeletal origin. The comparative active data for the Erchonia® red diode only therapy was attained in the 2001 trial whose results successfully supported 510(k) clearance (K012580) of application of the PL3000 red diode only for the identical indication being sought through the results of this clinical trial.

Forty-four (44) subjects completed the study. Subjects were predominantly Caucasian (82%) males (39%) and females (61%) of average age 54.07 years with chronic neck and/or shoulder pain of musculoskeletal origin due to osteoarthritis, chronic muscle spasms or cervical and thoracic spine sprain strain who rated 50 or greater on the 0 to 100 Visual Analog Pain Scale (VAS). Average subject duration of neck and shoulder pain was 76.58 months with the location of pain evenly distributed across the right and left sides. Average VAS pain rating at study entry

was 65.00. In the 2001 comparative trial, 43 subjects received the active Erchonia® EVRL red diode only procedure administration.

Each subject received a single 13-minute active procedure administration with the Erchonia® EVRL at the investigator's test site as in the 2001 trial, differing only in dual-diode (red and violet) versus single-diode (red only) application, respectively.

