Study primary outcome measure was change in Visual Analog Scale (VAS) neck and shoulder pain rating from baseline to study endpoint evaluation. Individual subject success criteria was established as a 30% or greater decrease in VAS rating at endpoint relative to baseline. The study was pre-established as a non-inferiority study (equivalency or superiority) of the EVRL in red/violet diode combination therapy compared to the red diode only therapy as based upon the comparative data from the 2001 trial. Overall study success criteria was established as 65±5% of individual subject successes in the current trial. Seventy-five per cent (75%) of subjects in this dual diode violet/red laser study attained individual subject success compared with 65.1% of actively treated subjects in the 2001 trial, exceeding the overall study success criteria by 5%. The 29.80-point mean decrease (from 65.00 to 35.20) in neck and shoulder VAS pain rating from study Baseline to Endpoint for subjects in the violet/red laser study was comparable to (slightly above) the respective 29.02-point mean decrease (from 60.21 to 31.19) for the 2001 Active study subjects. As in the 2001 red laser only study, no adverse or other safety events were reported or recorded across study duration.

It was concluded that the application of simultaneous violet and red laser light was non-inferior to the application of red laser light alone in providing adjunctive temporary relief of minor chronic neck and shoulder pain of musculoskeletal origin.

3. The above two Erchonia-sponsored clinical trial outcomes, in addition to the below two Erchonia-sponsored clinical trial outcomes provided primary support for clearance of the indication for '*adjunctive use in providing temporary relief of nociceptive musculoskeletal pain*' for the respective light therapy devices:

➤ **CHRONIC LOW BACK PAIN:**

➤ **CHRONIC PLANTAR FASCIITIS HEEL PAIN:**

STUDY JUSTIFICATION

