Subjects will be males and females 22 years or older who present with chronic (30 consecutive days or longer) neck and/or shoulder pain diagnosed as being of musculoskeletal origin (osteoarthritis, chronic muscle spasm, cervical and thoracic spine sprain strain) and with a self-reported pain level of 50 or greater on the 0 to 100 VAS.

Sample Size

There will be 43 qualified subjects enrolled in this study.

Rationale for Sample Size

Sample size is determined to be identical to that of subjects enrolled in the active treatment group that forms the comparative data reference group in this study.

Recruitment

Subjects will be recruited from among:

- (i) The Principal Investigator's/test site's pool of existing and new patients
- (ii) Referrals from other suitable medical clinics and professionals
- (iii) Subjects who respond to the recruitment materials shown in **Appendix A**.

Compensation

A subject will not receive financial or any other form of compensation to participate in this clinical study. However, he or she will also not be charged for the cost of the study treatment with the Erchonia lasers or for the cost of any other directly-related evaluations or measurements that occur as a directly-associated part of his or her participation in the study.

STUDY PROCEDURE

STUDY TEST BATTERY

The following are the study measurement and assessment tools to be used and the variables to be recorded in this clinical study. At each evaluation point, the precise tools and variables that will be employed will be specified.

QUALIFICATION EVALUATION TOOL

PHYSICAL EXAMINATION

- (i) Inspection: Manipulation of the neck, shoulders, and cervical spine to evaluate for knots (muscle spasms), tightness, swelling, osteophytes, etc.
- (ii) Palpation Assessment: Physical assessment of the bony and soft tissues of the neck, shoulder, and cervical spine through touch with the pads of the fingers, to evaluate for muscle tightness and knotting, trigger points that cause pain and possibly also radiating pain.

BASELINE VARIABLES

NECK/SHOULDER PAIN VARIABLES

- (i) Location of pain: right side/left side/back of neck; right/left shoulder
- (ii) Duration of pain: months/years since onset of first episode of neck/shoulder pain

CONCOMITANT MEDICATION AND THERAPY USE

- (i) Over the counter and prescription medications currently used to relieve neck/shoulder pain, including duration, dosage, and frequency of use

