- *Null Hypothesis:* Sequential treatment application of the Erchonia® PPL blue laser therapy followed by the standard Erchonia® red laser therapy using the XLR8 is inferior to treatment application of the Erchonia red laser therapy alone in reducing neck and shoulder nociceptive pain of musculoskeletal origin to the effect of 60% or fewer subjects attaining a 30% or greater reduction in neck and shoulder pain at study endpoint evaluation relative to baseline.

$H_0: P \leq 60\%$; where P = individual subject responder rate

- *Alternative Hypotheses:* Sequential treatment application of the Erchonia® PPL blue laser therapy followed by the standard Erchonia® red laser therapy using the XLR8 is NOT inferior to (i.e., is equivalent to or superior to) treatment application of the Erchonia red laser therapy only in reducing neck and shoulder nociceptive pain of musculoskeletal origin to the effect of greater than 60% of subjects attaining a 30% or greater reduction in neck and shoulder pain at study endpoint evaluation relative to baseline.

$H_1: P > 60\%$; where P = individual subject responder rate

Evaluation Time Point

Study endpoint evaluation was preestablished as occurring immediately (within 3 minutes) following completion of administration of the second component of the sequential study treatment with the standard Erchonia® red light laser device. Study primary success analysis is preestablished at study endpoint relative to baseline, identically to that in the 2001 reference comparative study.

Change Scores

- T-test analysis of the difference in the mean change in VAS levels from baseline to endpoint between the dual-diode and red only diode treatment administration groups. Significance levels will be considered at the $p < 0.05$ level.
- A t-test for two independent sample will be performed to evaluate the significance of the difference in the mean change in VAS pain scores from baseline to endpoint evaluation between the two study groups to evaluate for equivalency to support the support the conclusion of the proportion of successes evaluation. Significance levels will be considered at the $p < 0.05$ level.

SECONDARY EVALUATIONS

The following secondary evaluations will be performed on the per protocol study data set only. As no claims are intended to be made based on secondary measures, the findings will be presented through descriptive analysis and qualitative trending only, without evaluation for or claims of statistical significance.

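### The supportive t-test on mean VAS change tests for a difference but is assigned to show equivalence, with no margin or confidence-interval rule on the VAS scale

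*Combined protocol and SAP*

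**What the plan says.** The Change Scores part of the Statistical Analysis Plan has two bullets that describe the same analysis. The second reads "A t-test for two independent sample will be performed to evaluate the significance of the difference in the mean change in VAS pain scores". It goes on to give the groups compared and the purpose of the test: "between the two study groups to evaluate for equivalency to support the support the conclusion of the proportion of successes evaluation". The decision threshold is "Significance levels will be considered at the $p < 0.05$ level"; sidedness is not stated. Neither bullet names a covariate, a margin on the VAS scale, or a confidence interval.

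Change Scores stands under the primary efficacy outcome heading and before Secondary Evaluations. The statement that secondary measures are descriptive, with no significance testing, therefore does not cover it.

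The only margin in the plan is in Justification for Study Success Criteria: 5 percentage points on the responder proportion, so that non-inferiority requires at least 60% responders. The hypotheses are written on that proportion alone.

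On numbers, the Sample Size section says "There will be 43 qualified subjects enrolled in this study", and the supporting-data section says "In the 2001 comparative trial, 43 subjects received the active Erchonia® EVRL red diode only procedure administration". The rationale for sample size is matching to that group; no power, effect size or SD is given. The Randomization section states that the trial is non-randomised.

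**The concern.** A t-test of difference takes zero difference as its null hypothesis. Failing to reject it says that the data are compatible with no difference; it does not say that they exclude a difference large enough to matter. Smaller or noisier samples make failure to reject more likely, so a reader who takes p≥0.05 as support gives more credit to weaker data. To evaluate equivalence or non-inferiority on mean VAS change, the plan needs a largest tolerable deficit on that scale and an interval that excludes it. It has neither.

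What is at stake is the weight of the supporting evidence. The primary hypothesis sets the new group against a fixed 60%. The t-test is thus the only efficacy test in the plan that compares the data of the two groups directly, and a non-significant result could be presented as independent corroboration of non-inferiority without having that content.

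A second, smaller issue is that the comparison is with a historical group and uses unadjusted change. Nothing in the design balances baseline VAS between the two studies.

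**Working it through.** **Inputs.** From the documents: n = 43 in each group; mean change in the 2001 red-only group 29.02 points; threshold 0.05. Assumed: a two-sided test; a common SD of change of 15, 20 or 25 points; true deficits of 5 and 8 points as illustrations, since the documents define no clinically important VAS difference. An 8-point deficit is 8/29.02 = 28% of the 2001 mean change.

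**Plan's own figures.** The sample size of 43 cannot be derived, because it is matched and not calculated. The reported mean changes do reproduce: 60.21 − 31.19 = 29.02 and 65.00 − 35.20 = 29.80.

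**Is the SD range plausible?** The 2001 trial reports p<0.0005 for active v placebo with 86 subjects analysed. Taking 43 per group and a two-sided p-value, the pooled SD must be below about 31 if the difference is 29.02 − 4.91 = 24.11, or below about 26 if it is the printed 20.08. The assumed range fits under both bounds.

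**Chance of a non-significant result when the new regimen is truly worse.** The standard error is SE = SD × √(2/43). With true deficit d, the normal approximation is P(non-significant) ≈ Φ(1.96 − d/SE); the other tail is negligible. The 95% half-width uses the t critical value 1.989 on 84 degrees of freedom.

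| SD (assumed) | SE | 95% half-width | d = 5 | d = 8 |
|---|---|---|---|---|
| 15 | 3.23 | 6.4 | 0.66 | 0.30 |
| 20 | 4.31 | 8.6 | 0.79 | 0.54 |
| 25 | 5.39 | 10.7 | 0.85 | 0.68 |

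Example at SD 20, d = 8: 8/4.31 = 1.855; Φ(1.96 − 1.855) = Φ(0.105) = 0.54. The exact noncentral t calculation gives 0.67/0.79/0.85 for 5 points and 0.31/0.55/0.69 for 8 points, so the approximation is adequate.

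**Effect of sample size.** At SD 20 and a true 10-point deficit, the chance of non-significance is 37% with 43 per group, 66% with 20 and 82% with 10. The less data, the easier the apparent support.

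**Baseline.** The supporting-data section gives, for the violet/red study, "The 29.80-point mean decrease (from 65.00 to 35.20) in neck and shoulder VAS pain rating" and, for the comparator, "29.02-point mean decrease (from 60.21 to 31.19) for the 2001 Active study subjects". Both studies required VAS of 50 or more at entry, yet mean baselines differ by 65.00 − 60.21 = 4.79 points. A baseline gap of that size can therefore occur under the same entry rule.

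**The case against.** The strongest reply is that the test does not decide the trial. Success rests on the responder rate, which is already defined relative to each subject's own baseline. A regimen that is materially worse on mean VAS would usually also produce fewer responders, so a misleading t-test matters only when the primary rule is met as well; the probabilities above are for the t-test alone. This stands, and it limits the weight of the point.

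Three stronger readings are tempting, and the documents do not support them.

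- *The plan treats non-significance as proof of equivalence.* No sentence says so. The reading is an inference from the purpose clause, though no other rule is offered. What is certain is that the decision rule is undefined.
- *The test can corroborate the primary result only through low power.* This is not so. The stated aim covers equal or superior, so a significant advantage for the new regimen would also corroborate, and a non-significant result may reflect a truly small difference. Large deficits would usually be found: at SD 20, a 15-point deficit is significant about 93% of the time.
- *Baseline imbalance reversed the violet/red comparison.* Raw change favoured violet/red by 29.80 − 29.02 = 0.78 points, while endpoint pain was 35.20 − 31.19 = 4.01 points higher and the ratio of mean change to mean baseline was lower (29.80/65.00 = 45.8% v 29.02/60.21 = 48.2%). But 0.78 is far inside a half-width of 6.4 to 10.7, the percentages are ratios of group means, and the baseline-relative responder rates in the same section (75% v 65.1%) favour violet/red, as raw change does. An adjusted endpoint difference, 4.01 − b × 4.79, favours red-only only if the baseline slope b is below 4.01/4.79 = 0.84, and no slope is reported. It is also a different study from this one.

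It is also fair to say that covariance adjustment is not a plain correction here. In non-randomised groups, change scores and ANCOVA rest on different untestable assumptions, and neither removes historical-control bias.

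**Conclusion.** The point holds as a mismatch between method and purpose. A difference test at p<0.05 is assigned to evaluate equivalency, and mean VAS change has neither a margin nor an interval rule. If p≥0.05 were read as support, a true 5-point deficit would pass about 66% to 85% of the time and an 8-point deficit about 30% to 68%, at 43 v 43 with a two-sided test and an SD of 15 to 25 points. The SD and the deficits are assumptions, so these figures illustrate and do not predict.

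The analysis is supportive and cannot by itself make the trial succeed. On baseline, the documents show only that mean VAS can differ between studies with the same entry rule. That is enough reason to report an adjusted estimate alongside the unadjusted one, but not to say that the earlier comparison was reversed or that this one will be. The point should be fixed because it changes what may be concluded, and the change is nearly free.

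**What to change.** Amend Change Scores as follows.

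1. Merge the two bullets into one analysis: the difference in mean VAS change between groups with its two-sided 95% confidence interval.
2. Delete the words that give evaluating equivalency as the purpose, and state that p≥0.05 is not evidence of equivalence.
3. State that the result is descriptive unless a justified margin on mean VAS change is fixed before data are seen and the interval excludes a deficit beyond it.
4. Report a baseline-VAS-adjusted difference (ANCOVA) beside the unadjusted one if subject-level 2001 data are available. The Blinding section, under which both datasets go to the statistician de-identified, suggests that they are. Say that adjustment does not remove historical-control bias.

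The cost is plan wording; baseline VAS is already collected. The downside is that the analysis can no longer be cited as showing equivalence and may be inconclusive at 43 per group. With a true difference of zero and a one-sided 2.5% test, power at SD 15/20/25 is 33%/21%/15% for an illustrative 5-point margin and 86%/63%/45% for 10 points. The documents give no VAS margin, and these two are not recommendations. If none can be justified, the descriptive label is the practical choice.

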The treatment administration protocol with the red laser device in this current study is identical to that which was evaluated in the comparative retrospective study to enable direct comparison of findings between the two studies and statistical analysis of different group outcomes. The only modification in the current study is the addition of a 5-minute treatment with the Erchonia PPL laser, administered immediately prior to the red laser therapy which is the treatment arm being evaluated for non-inferiority.

TREATMENT ADMINISTRATION PHASE EVALUATIONS: STUDY ENDPOINT

Within three (3) minutes of completion of the procedure administration phase, study endpoint evaluation will occur.

OUTCOME ASSESSMENTS

- Visual Analog Scale (VAS) Degree of Pain Rating
- Linear Range of Motion (ROM)
- Subject Satisfaction with Study Outcome Rating
- Adverse Events Evaluation

POST-TREATMENT ACTIVITIES

The post-treatment evaluation phase of this study will commence immediately following completion of the treatment administration phase evaluations and will last for two (2) days (48 hours).

The post-treatment outcome assessments will be recorded by the subject in his or her own home on forms provided by the test site. The subject will be instructed on when and how to complete the forms and how to return them to the test site prior to leaving the test site on the treatment administration day.

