24 HOURS AND 48 HOURS POST-TREATMENT EVALUATIONS

The subject will be required to record the following at home on the forms provided by the test site at 24 hours and again at 48 hours after completion of the treatment administration phase at the test site.

OUTCOME ASSESSMENTS

- Visual Analog Scale (VAS) Degree of Pain Rating
- Linear Range of Motion (ROM)
- Subject Satisfaction with Study Outcome Rating
- Adverse Events Evaluation

STATISTICAL ANALYSIS PLAN

Populations Examined

Two (2) subject populations will be analyzed, as applicable:

- (i) **Intent-to-Treat (ITT) Population:** All enrolled subjects regardless of whether any measures are recorded and/or treatment is administered.
- (ii) **Per-Protocol (PP) Population:** All enrolled subjects who completed the study per protocol through to the 48-hour post-treatment evaluation, excluding subjects with major protocol deviations, incompletes, etc.

Primary analysis of efficacy will be according to the intent to treat (ITT) population and the secondary supportive analysis will be according to the per protocol (PP) population. Non-inferiority will be established if both the ITT and PP analyses agree.

Handling of Missing Data

Missing data will be handled through multiple imputation analysis, a strategy to handle missing values in a clinical trial wherein each missing value is replaced with a set of plausible values that represent the uncertainty about the right value to impute. The exact method of multiple imputation analysis will be determined after study completion depending on factors such as the amount of missing data and whether it is determined that the data are missing at random (MAR) or missing not at random (MNAR).

PRIMARY EFFICACY OUTCOME MEASURE: CHANGE IN SUBJECT SELF-REPORTED VAS PAIN RATING FROM BASELINE TO STUDY ENDPOINT

The aim of this study is to determine if the treatment effect of the sequential therapy with the Erchonia® PPL blue laser therapy followed by the Erchonia® XLR8 standard red laser therapy for the active treatment group in this study is equal to or superior to that attained for the active comparative treatment group in the comparative reference study who received the standard red laser therapy alone.

Proportion of Successes

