- Change in mean neck and shoulder pain VAS ratings across study duration: baseline, endpoint, 24 hours, and 48 hours post-procedure.
- Change in linear ROM measurements at study endpoint relative to baseline.
- Subject satisfaction with study outcome ratings across study duration.

INDIVIDUAL TEST SITES

Results will be presented by individual test site for comparison.

INDIVIDUAL SUBJECT RESULTS

Individual subject results for the primary study outcome measure will also be presented.

SAFETY ANALYSIS

Safety analysis will be based on all enrolled subjects and will be assessed by evaluating and comparing the frequency and incidence of observed and/or reported adverse events between subjects enrolled in the current study and subjects enrolled in the comparative reference study. A chi-square test with a continuity correction will be performed to compare the percentage of subjects who had adverse events between the two subject groups.

ADVERSE EVENTS

At each evaluation and measurement point throughout the clinical study, and at any other time throughout the duration of the clinical trial that is necessary, all potential adverse events reported by a subject or observed by an investigator will be recorded on the case report form, and subsequently evaluated by the investigator for its relation to the study procedure and whether any corrective action needs to be taken. All potential adverse events recorded will be appropriately reported to the governing IRB, as applicable.

It is unlikely and not expected that any adverse events will result from implementation of this clinical study protocol. Prior clinical trials evaluating application of Erchonia low level laser light, including numerous evaluating Erchonia lasers for the treatment of various pain conditions, including neck and shoulder nociceptive pain of musculoskeletal origin, have not typically yielded any adverse events or reactions.

ADVERSE EVENTS DEFINITION

An adverse event means any untoward medical occurrence associated with the use of an intervention in humans, whether or not considered intervention-related (21 CFR 312.32 (a)).

SERIOUS ADVERSE EVENTS (SAE) DEFINITION

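### Restricting every secondary evaluation to 48-hour per-protocol completers discards valid on-site and returned home data because of later events, and may make the descriptive results look too favourable

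*Combined protocol and SAP*

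**What the plan says.** Under Secondary Evaluations the SAP states: "The following secondary evaluations will be performed on the per protocol study data set only". Three items follow:

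- VAS: "Change in mean neck and shoulder pain VAS ratings across study duration: baseline, endpoint, 24 hours, and 48 hours post-procedure".
- ROM: "Change in linear ROM measurements at study endpoint relative to baseline".
- Satisfaction: "Subject satisfaction with study outcome ratings across study duration".

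Populations Examined defines the per-protocol set as "All enrolled subjects who completed the study per protocol through to the 48-hour post-treatment evaluation, excluding subjects with major protocol deviations, incompletes, etc". The intent-to-treat set, "All enrolled subjects regardless of whether any measures are recorded and/or treatment is administered", carries the primary analysis but is not used for the secondary items.

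On timing, the section on treatment-phase evaluations says: "Within three (3) minutes of completion of the procedure administration phase, study endpoint evaluation will occur". Endpoint ROM and the first satisfaction rating are collected at that moment. Under Post-Treatment Activities, the 24- and 48-hour assessments are completed by the subject at home and sent back. Secondary Evaluations adds that the results are descriptive and that no claim will rest on them.

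**The concern.** An analysis set should not depend on what happens after the outcome was measured. Here it does. A subject with complete endpoint ROM and a first satisfaction rating disappears from both results if the 48-hour evaluation is not completed, or if a major deviation occurs in the meantime. A subject who returned a 24-hour form but not the 48-hour one loses the 24-hour data too.

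Some of these later events may be linked to outcome. Inclusion criteria 8 and 9 require subjects to be willing and able to go without pain medication and other neck or shoulder therapy while in the study, so a subject whose pain returns and who treats it may be counted as a deviator. A dissatisfied subject may be less likely to send back a form. Where such links exist, the retained subjects look better than the treated group as a whole.

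What is at stake is the description of how pain, ROM and satisfaction behave after treatment. The 24- and 48-hour VAS ratings are this trial's only pain ratings after the endpoint, in a study of temporary relief.

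**Working it through.** **Which data are lost**

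| Secondary item | When measured | Condition for being reported |
|---|---|---|
| ROM, endpoint versus baseline | On site, no later than 3 minutes after treatment | Completion to 48 hours, no major deviation |
| Satisfaction, first rating | Same | Same |
| VAS and satisfaction at 24 hours | At home | Same |
| VAS and satisfaction at 48 hours | At home | Same |

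In the first three rows the condition is settled after the measurement. In the fourth, a subject who returned the form but had a major deviation is still removed.

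**Whether another provision restores the data**

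- Multiple imputation (Handling of Missing Data) does not bring back subjects whom the per-protocol definition has already removed.
- The intent-to-treat rule covers the primary VAS endpoint, and safety uses all enrolled subjects. Neither covers ROM, satisfaction or the 24/48-hour VAS.
- Individual subject results are promised only for the primary measure, so a reader could not rebuild the secondary results.

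**Inputs for an illustration of size**

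- Planned N = 43 (Sample Size), set equal to the 2001 active group. The plan's figures are consistent: 86 analysed / 2 arms = 43, and 28/43 = 65.1% matches the reported active success rate.
- Mean VAS fall = 29.02 points (2001 active group): 60.21 − 31.19 = 29.02. This was measured immediately after treatment. The documents give no 24- or 48-hour figure, so it is borrowed for scale only.
- Number excluded, d: not stated. Assumed 2 to 9 of 43 (4.7% to 20.9%).
- Mean fall in excluded subjects, m: not stated. Assumed 0, 15 or 29.02 points.

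**Formula**

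All-subject mean fall = [29.02 × (43 − d) + m × d] / 43.

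Overstatement = 29.02 − all-subject mean fall = (d/43) × (29.02 − m).

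| d | All-subject fall if m = 0 | Overstatement, m = 0 | Overstatement, m = 15 | Overstatement, m = 29.02 |
|---|---|---|---|---|
| 2 | 27.67 | 1.35 | 0.65 | 0 |
| 4 | 26.32 | 2.70 | 1.30 | 0 |
| 6 | 24.97 | 4.05 | 1.96 | 0 |
| 9 | 22.95 | 6.07 | 2.93 | 0 |

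Example, d = 4 and m = 0: 29.02 × 39 / 43 = 26.32, and 29.02 − 26.32 = 2.70.

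**Satisfaction**

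Assume 31 of 39 per-protocol subjects are satisfied (79.5%) and 4 are excluded. The figure for all 43 then lies between 31/43 = 72.1% (none of the four satisfied) and 35/43 = 81.4% (all four satisfied). The per-protocol figure could err in either direction.

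**The case against.** The strongest reply is that little depends on these results. They are descriptive, carry no claim or test, and feed no success criterion. The primary endpoint is analysed by intent to treat with per protocol in support, and safety uses everyone enrolled. This stands, and it keeps the point minor. It does not remove bias from a reported mean.

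A reader might go further and infer that the rule drops the subjects who did worst, so that relief is bound to look more durable than it was. The documents do not support that. They give no exclusion rate and no reasons for non-return, and a form can go missing for unrelated reasons or because the subject felt well. The medication rule appears as an entry criterion of willingness, major deviation is not defined, and nothing in the plan classes analgesic use after treatment as major. Exclusion related to poor outcome is plausible, not established.

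The illustration is open to the same criticism. It applies an immediate post-treatment fall to a question partly about 24 and 48 hours, and its upper figures assume no improvement at all in excluded subjects. No single figure from the table should be quoted without the range, which starts at zero.

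Finally, an observed-data analysis cannot recover forms that were never returned. Subjects who took an analgesic and did return forms may have lower VAS for that reason, so including them could make the course look better. Both limits stand for the 24/48-hour data. Neither applies to the on-site ROM and first satisfaction rating.

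**Conclusion.** The point holds as a minor weakness in the analysis-set rule. The plan discards valid endpoint ROM, first satisfaction ratings and returned home ratings because of later events that may be related to outcome, and it provides no alternative presentation. That follows from the wording alone.

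The size cannot be computed from the documents. On the assumptions above, with 2 to 9 of 43 excluded, the mean VAS fall would be overstated by 0 points if exclusion is unrelated to outcome, and by about 1.4 to 6.1 points if excluded subjects show no change. The direction of any bias is an expectation, not a finding. The primary and safety conclusions do not change.

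**What to change.** Replace the per-protocol restriction in Secondary Evaluations with a statement that:

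- each secondary item is presented for all treated subjects with observed data at that time point;
- n is shown at each time point, with reasons for exclusion or missingness;
- analgesic use after treatment is flagged, since it may itself lower VAS;
- the per-protocol version is shown as a supplement.

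It would also help to define major deviation before the data are reviewed.

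This fully restores the three-minute data and partly restores the 24/48-hour data. Forms never returned stay missing, and the displayed n makes that visible. The cost is one line of SAP wording and one extra set of descriptive tables. No new data or subjects are needed.
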